9.5. Randomization and Blinding

No blinding will be needed as this is an open-label study.

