13.2.2. Efficacy Analysis

The efficacy outcome measures will be measured at Baseline, Months, 1, 3, 6, 9, and 12 which is end of study or early termination; and include:

- YGTSS-TTS, which is the combined score from the motor and phonic tic score,
- YGTSS Impairment score and global YGTSS (YGTSS-TTS + Impairment score),
- CGI-TS-S
- CGI-TS-I (not measured at Baseline)

The observed YGTSS-TTS, YGTSS-Global and CGI values and their changes from baseline will be summarized by visit. The paired t-test may be used for analyzing the change from baseline within treatment.

The CGI-TS-S, CGI-TS-I and C&A-GTS-QOL values will also be summarized descriptively by visit as continuous and categorical variables.

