6.1. General Methods

All analyses and outputs will be produced using SAS® version 9.4 or later. Continuous variables will be summarized using the number of observations (n), mean, standard deviation (SD), median, minimum, and maximum. Categorical variables will be summarized using frequency counts (n), and percentages.

All relevant subject data will be included in listings. All subjects entered the database will be included in subject data listings. All by visit summaries will use the nominal visit. Unscheduled visits will not be summarized but will be included in the listings.

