6.4. Visit Windows

The following visit windows will be used in the summarization or analysis of safety laboratory, vital signs, ECG, and physical exam data. If more than 1 data point falls within the window, then the data point

This document is confidential.

closest to the target day will be used. If there are 2 data points equidistant to the target day, one high and one low, then the high data point will be used. Visit windowing will not be applicable to follow-up visits.

If Baseline is Day 1, then:

Month 1 (target day = 29) 2 - 42

Month 2 (target day = 57) 43 - 70

Month 3 (target day = 85) 71 - 98

Month 4 (target day = 113) 99 - 126

Month 5 (target day = 141) 127 - 154

Month 6 (target day = 169) 155 - 182

Month 7 (target day = 197) 183 - 210

Month 8 (target day = 225) 211 - 238

Month 9 (target day = 253) 239 - 266

Month 10 (target day = 281) 267 - 294

Month 11 (target day = 309) 295 - 322

Month 12 (target day = 337) 323 and above (and not a follow-up visit)

For all efficacy and safety scales a modified last observation carried forward (LOCF) approach will be used to reassign Early Termination visits. Early Termination visits will be assigned to the next scheduled visit (per Schedule of Assessments for the parameter) after a subjects' latest scheduled visit before early termination.

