9.9. COVID-19 Analyses

Due to COVID-19 pandemic, additional analyses will be conducted:

- Listings of COVID-19 related study disruptions by subject and by site, including descriptions of the disruption.
- Protocol deviations due to COVID-19 will be summarized by type in a table.

This document is confidential.

10. Changes from Analysis Planned in Protocol

As per protocol, the Modified Intention-to-Treat (mITT) set was defined as all subjects who receive at least one dose of study drug which is same as the safety population set. Hence the mITT set definition was updated as 'all subjects who receive at least one dose of study drug and have at least one post Baseline scoring of YGTSS'.

Following updates and additional analysis were included in the SAP after the data base lock.

- An additional analysis set, Intention-to-Treat (ITT) Set, was defined as all enrolled subjects. All efficacy analysis will also be conducted using the ITT population.
- Visit windowing will be used in the summarization or analysis of safety laboratory, vital signs, ECG, and physical exam data.
- For all efficacy and safety scales a modified last observation carried forward (LOCF) approach will be used to reassign Early Termination visits. Early Termination visits will be assigned to the next scheduled visit (per Schedule of Assessments for the parameter) after a subjects' latest scheduled visit before early termination.
- Demographics and baseline characteristics will also be summarized by treatment group (ecopipam, placebo, overall) from CL (EBS-101-CL-001) study in the mITT Set (Table 14.1.3.1a), and be also summarized for the ITT Set (Table 14.1.3.1b).
- Medical history will also be summarized by treatment group (ecopipam, placebo, overall) from CL (EBS-101-CL-001) study in the Safety Set (Table 14.1.3.2a).
- Extent of exposure summary by days will be provided as well (Table 14.1.5a).
- YGTSS-TTS will also be summarized by treatment group (ecopipam, placebo and overall) from CL (EBS-101-CL-001) study (Tables 14.2.1.1.1a).
- Efficacy summaries for the ITT Set will be generated (Tables 14.2.1.1.1b, 14.2.1.1.2b, 14.2.1.1.3b, 14.2.1.1.4b, 14.2.1.2b, 14.2.1.3b, and 14.2.1.4b).
- A summary of the percent of subjects with a 25% or greater improvement on the YGTSS-TTS in mITT set will be provided (Table 14.2.1.1.5).
- A summary of the most common ($\geq 5\%$) AEs first onset by month will be provided in Table 14.3.1.9.1 and by month (new incidence or ongoing) in Table 14.3.1.9.2.

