	14.1.4.2	Concomitant Medications Summary	Safety Set
	14.1.5	Extent of Exposure Summary	Safety Set
	14.1.5a	Extent of Exposure Summary	Safety Set
	14.1.6	Treatment Compliance Summary	Safety Set
14.2		Efficacy Data Summary Tables	
	14.2.1.1.1	YGTSS-TTS: Summary	miITT Set
	14.2.1.1.1a	YGTSS-TTS: Summary by Treatment Group (CL)	miITT Set
	14.2.1.1.1b	YGTSS-TTS: Summary	ITT Set
	14.2.1.1.2	YGTSS-TTS: Subscales Summary	miITT Set
	14.2.1.1.2b	YGTSS-TTS: Subscales Summary	ITT Set
	14.2.1.1.3	YGTSS-GS: Summary	miITT Set
	14.2.1.1.3b	YGTSS-GS: Summary	ITT Set
	14.2.1.1.4	YGTSS-Impairment: Summary	miITT Set
	14.2.1.1.4b	YGTSS-Impairment: Summary	ITT Set
	14.2.1.1.5	YGTSS-TTS: Subjects with a >= 25% Improvement	miITT Set
	14.2.1.2	CGI-TS-S: Summary	miITT Set
	14.2.1.2b	CGI-TS-S: Summary	ITT Set
	14.2.1.3	CGI-TS-I: Summary	miITT Set
	14.2.1.3b	CGI-TS-I: Summary	ITT Set
	14.2.1.4	C&A-GTS-QOL: Summary	miITT Set
	14.2.1.4b	C&A-GTS-QOL: Summary	ITT Set
14.3		Safety Data Summary Tables	
14.3.1		Adverse Events	
	14.3.1.1	Overall Summary of Adverse Events	Safety Set

This document is confidential.

Header	Table Number	Name	Analysis Set
	14.3.1.2.1	Summary of Adverse Events by Maximum Severity	Safety Set
	14.3.1.2.2	Summary of Adverse Events by Maximum Relatedness	Safety Set
	14.3.1.3.1	Summary of Adverse Events by System Organ Class and Preferred Term	Safety Set
	14.3.1.3.2	Summary of Adverse Events by System Organ Class, Preferred Term and Highest CTCAE Grade	Safety Set
	14.3.1.4.1	Summary of Treatment-Related Adverse Events by System Organ Class and Preferred Term	Safety Set
	14.3.1.4.2	Summary of Treatment-Related Adverse Events by System Organ Class, Preferred Term and Highest CTCAE Grade	Safety Set
	14.3.1.5.1	Summary of Adverse Events Leading to Treatment Termination by System Organ Class and Preferred Term	Safety Set
	14.3.1.5.2	Summary of Adverse Events Leading to Treatment Termination by System Organ Class, Preferred Term and Highest CTCAE Grade	Safety Set
	14.3.1.6	Summary of CTCAE Grade 3 or Higher Adverse Events by System Organ Class and Preferred Term	Safety Set
	14.3.1.7.1	Summary of Serious Adverse Events by System Organ Class and Preferred Term	Safety Set
	14.3.1.7.2	Summary of Serious Adverse Events by System Organ Class and Preferred Term by Age Group	Safety Set
	14.3.1.8.1	Summary of Adverse Events of Special Interest (AESI) for Parkinsonism by System Organ Class and Preferred Term	Safety Set

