	14.3.1.8.2	Summary of Adverse Events of Special Interest (AESI) for Ecopipam by System Organ Class and Preferred Term	Safety Set
	14.3.1.9.1	Summary of Most common (>=5%) Adverse Event First Onset by Month	Safety Set
	14.3.1.9.2	Summary of Most common (>=5%) Adverse Events by Month (new incidence or ongoing)	Safety Set
14.3.4.1		Clinical Laboratory Data	

This document is confidential.

Header	Table Number	Name	Analysis Set
	14.3.4.1.1.1	Clinical Laboratory Results Summary: Hematology	Safety Set
	14.3.4.1.1.2	Shift from Baseline Summary: Hematology	Safety Set
	14.3.4.1.2.1	Clinical Laboratory Results Summary: Serum Chemistry	Safety Set
	14.3.4.1.2.2	Shift from Baseline Summary: Chemistry	Safety Set
	14.3.4.1.3.1	Clinical Laboratory Results Summary: Urinalysis	Safety Set
	14.3.4.1.3.2	Shift from Baseline Summary: Urinalysis	Safety Set
	14.3.4.1.4.1	Clinical Laboratory Results Summary: HbA1c	Safety Set
	14.3.4.1.4.2	Shift from Baseline Summary: HbA1c	Safety Set
14.3.4.2		Vital Signs	
	14.3.4.2.1	Vital Signs Summary	Safety Set
14.3.4.3		Electrocardiogram (ECG) Data	
	14.3.4.3.1	12-Lead Electrocardiogram Summary	Safety Set
	14.3.4.3.2	12-Lead Electrocardiogram Overall Interpretation Summary	Safety Set
14.3.4.4		Abnormal Physical Examination Results by Visit	
	14.3.4.4.1	Physical Examination Summary	Safety Set
14.3.4.5		Other Safety Data	
	14.3.4.5.1	Summary of Columbia Suicide Severity Rating Scale (C-SSRS)	Safety Set
	14.3.4.5.2	Summary of Abnormal Involuntary Movement Scale (AIMS) Total Score	Safety Set
	14.3.4.5.3	Summary of Barnes Akathisia Rating Scale (BARS)	Safety Set
	14.3.4.5.4	Summary of Children's Depression Rating Scale – Revised (CDRS-R) Raw Summary Score	Safety Set
	14.3.4.5.5	Summary of Pediatric Anxiety Rating Scale (PARS) Total Score	Safety Set
		Post-Hoc Analysis	
	14.3.4.6a	Shift from Baseline Summary: BMI z-score	Safety Set
	14.3.4.6b	Shift from Baseline Summary: Height z-score	Safety Set
	14.3.4.6c	Shift from Baseline Summary: Weight z-score	Safety Set
	14.3.4.7a	Shift from Baseline Summary: 12-Lead Electrocardiogram QTC	Safety Set
	14.3.4.7b	12-Lead Electrocardiogram Outliers	Safety Set

This document is confidential.

Statistical Analysis Plan for Interventional Studies

Sponsor: Emalex Biosciences, Inc.; Protocol No.: EBS-101-OL-001

Header	Table Number	Name	Analysis Set
	14.3.4.7c	Vital Sign: Heart Rate Outliers	Safety Set
	14.3.4.8	Shift from Baseline Summary: HbA1c	Safety Set

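### Two visit-assignment rules were added after database lock of an open-label study; they conflict with the nominal-visit rule still in the SAP, have no comparison tables, and 15 of the 23 post-lock tables are not labelled post hoc

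*SAP*

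**What the plan says.** - **Timing.** SAP Section 10 introduces its list with "Following updates and additional analysis were included in the SAP after the data base lock". Protocol 9.5 says "No blinding will be needed as this is an open-label study".
- **Windows.** One entry reads "Visit windowing will be used in the summarization or analysis of safety laboratory, vital signs, ECG, and physical exam data". SAP 6.4 gives the day ranges.
- **ET rule.** For all efficacy and safety scales, Section 10 and SAP 6.4 adopt what they call a modified last-observation-carried-forward approach: "Early Termination visits will be assigned to the next scheduled visit (per Schedule of Assessments for the parameter"). Section 6.4 presents this and the windows as the working rules, with no post-hoc label.
- **General rule.** SAP 6.1 still says "All by visit summaries will use the nominal visit".
- **Protocol.** Section 13.2.2 lists the efficacy time points and ends with Month "12 which is end of study or early termination". Table 2 gives End of Study and Early Termination one column, at Month 12.
- **Index.** SAP Section 14 has one heading, "Post-Hoc Analysis", over the last eight tables. The responder table, "YGTSS-TTS: Subjects with a >= 25% Improvement", is listed above it among the other efficacy tables.

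**The concern.** Most post-lock entries add a table. The two visit rules do more: they decide which value enters each row of tables that were already planned. The windows act on laboratory, vital-sign and ECG data, which serve the primary (safety) objective. The ET rule acts on the efficacy scales, which serve the secondary objective of durability, and on the safety scales. With locked open-label data, the effect of either rule on the results could have been known when it was chosen.

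A reader who wants to judge whether that matters needs the same tables under the other rule, and none is indexed. SAP 6.1 and 6.4 also give different instructions, so two programmers following the SAP could build different tables.

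The labelling problem is separate. A post-hoc heading over only some of the post-lock tables suggests that the rest were planned. SAP 12.2.3 identifies a display by number, title and analysis set, and SAP 12.2.6 asks for few footnotes, so a table read apart from Section 10 would not show when it was added.

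**Working it through.** The plan states no figure to reproduce here: there is no sample-size calculation, alpha or expected dropout. The check sets the texts side by side, counts the tables, and gives one illustration on stated assumptions.

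**1. Reach of each rule**

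| Post-lock rule | Applies to | Reaches YGTSS, CGI or C&A-GTS-QOL rows? |
|---|---|---|
| Day windows | Labs, vital signs, ECG, physical examination | No |
| ET reassignment | All efficacy and safety scales | Yes |

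**2. Where an ET score goes.** YGTSS is scheduled at Months 0, 1, 3, 6, 9 and 12. By last scheduled YGTSS visit, the ET score goes:

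- Baseline → Month 1
- Month 1 → Month 3
- Month 3 → Month 6
- Month 6 → Month 9
- Month 9 → Month 12

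Despite its name, the rule carries nothing past the next scheduled visit. Someone who leaves before Month 9 is absent from the Month 12 row.

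**3. What the rule replaced.** The pre-lock SAP is not supplied. Two readings fit the remaining text:

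- *ET pooled with Month 12*, as the shared column in Table 2 and the wording of Protocol 13.2.2 suggest.
- *ET as its own nominal visit*, which SAP 6.1 permits. Month 12 then holds no ET scores.

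Let D be the proportion leaving early, all with an ET score, and s the share of leavers whose last scheduled YGTSS visit was Month 9. The ET share of the Month 12 row is:

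- ET separate: 0
- Post-lock rule: D·s / (1 − D + D·s)
- ET pooled: D

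The documents give neither D nor s. Assume D = 20–40% and s = 10–40%:

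- Post-lock, lowest: 0.02 / (0.80 + 0.02) = 2.4%
- Post-lock, highest: 0.16 / (0.60 + 0.16) = 21.1%
- Pooled: 20–40%

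If leavers improved less than those reaching Month 12 by an assumed gap on YGTSS-TTS, the row mean lies share × gap away from the completer mean:

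| Assumed gap | ET separate | Post-lock rule | ET pooled |
|---|---|---|---|
| 3 points | 0 | 0.07–0.63 | 0.60–1.20 |
| 6 points | 0 | 0.15–1.26 | 1.20–2.40 |

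The post-lock rule lies between the two candidates. Against pooling it makes Month 12 look better; against a separate ET visit it makes Month 12 look worse.

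**4. Count of post-lock tables in Section 10**

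- Under the post-hoc heading: 3 z-score shifts, 2 ECG, 1 heart rate, 2 HbA1c/cholesterol = 8.
- Not under it: 2 demographics, 1 medical history, 1 exposure, 1 YGTSS-TTS by parent-study arm, 7 ITT efficacy, 1 responder, 2 adverse events by month = 15.
- Total 8 + 15 = 23, so 15/23 = 65% are unlabelled. Of the 15, 1 + 7 + 1 = 9 are efficacy and 6 are not.
- Also without such a label: 5 figures (14.2.1.4.1a–b, 14.3.4.6a–c) and 5 listings (16.2.4.1b, 16.2.6.1b, 16.2.6.2b, 16.2.6.3b, 16.2.9.1).

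The main mITT YGTSS-TTS table, 14.2.1.1.1, is not among the 23. It is a planned table whose visit rule changed.

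**The case against.** **The sponsor disclosed everything.** Section 10 lists both rules and names each added table, figure and listing as post-lock. This stands, and it rules out any suggestion of concealment. What remains is that 6.4 and the index do not carry the disclosure through. The index says that titles may still change, so the labels can be added.

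**A specific rule overrides a general one.** A programmer could take 6.4 as an exception to 6.1. That is reasonable, but 6.1 covers all by-visit summaries and mentions no exception, so the SAP should say so.

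**The ET rule is defensible and may be better than pooling.** Pooling would put the score of someone who left in Month 2 into the 12-month row and mix lengths of exposure. This stands. The documents do not support requiring a pooled Month 12/ET table as the main one. Protocol 13.2.2 and Table 2 say when assessments take place, not that every ET score is analysed as Month 12.

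**Efficacy is secondary and descriptive.** There is no stated alpha or hypothesis, and early leavers still appear in earlier rows, the listings and the disposition table. This limits the severity. It does not remove the need to show whether the durability result depends on the rule.

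**Conclusion.** The point holds as one of transparency and sensitivity, and it should be fixed. Two operating rules came in after lock, they conflict with SAP 6.1, no indexed table shows the alternative, and 15 of 23 post-lock tables, 5 figures and 5 listings lack a post-hoc label. These findings come from the documents alone and need no assumption.

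A reader might infer three stronger things that the documents do not support:

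- *That results drove the rules.* Section 10 proves when they were added, not why. Influence by the data cannot be excluded, and no more can be said.
- *That the ET rule removed poor responders from Month 12 and flattered durability.* That requires ET to have been pooled with Month 12 before lock, which is not established. Under the other reading the rule adds late leavers to the row. The shifts in the illustration depend entirely on the assumed dropout, timing and gap.
- *That the unlabelled tables make the Month 12 row pass as planned.* The two defects are independent: Table 14.2.1.1.1 is not one of the 15, six of the 15 hold no efficacy data, and the windows never touch the efficacy scales.

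**What to change.** 1. Reconcile SAP 6.1 with 6.4: state which data use the nominal visit, which use windows, and how ET visits are handled.
2. Produce the by-visit efficacy and safety tables under the nominal-visit rule, with ET handling stated, beside the windowed and reassigned versions. Label the latter post hoc. Say in the durability statement whether the Month 12 result depends on the rule.
3. Mark both rules, all 23 tables, the 5 figures and the 5 listings as added after database lock, in the index and on each display.

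The cost is a re-run of existing programs with another visit variable, plus footnotes. The sponsor also accepts that the Month 12 figure may look less favourable or less certain.

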12.1. General Considerations

- One SAS program can create several outputs.
- Each output will be stored in a separate file.
- Output files will be delivered in Word format or portable document format pdf.
- Numbering of tables, figures, and listings (TFL) will follow ICH E3 guidance (or other logical order for studies performed according to GCP)

12.2. Table, Listing, and Figure Format

12.2.1. General

- All TFLs will be produced in landscape format, unless otherwise specified.
- All TFLs will be produced using the Courier New font, size 8.
- The data displays for all TFLs will have a minimum blank 1-inch margin on all 4 sides.
- Headers and footers for figures will be in Courier New font, size 8.
- Legends will be used for all figures with more than 1 variable, group, or item displayed.
- TFLs will be in black and white (no color), unless otherwise specified.
- Specialized text styles, such as bolding, italics, borders, shading, and superscripted and subscripted text, will not be used in the TFLs, unless otherwise specified. On some occasions, superscripts 1, 2, or 3 may be used (see below).
- Only standard keyboard characters will be used in the TFLs. Special characters, such as non-printable control characters, printer-specific, or font-specific characters, will not be used. Hexadecimal-derived characters will be used, where possible, if they are appropriate to help display math symbols (e.g., μ). Certain subscripts and superscripts (e.g., cm^2 , C_{max}) will be employed on a case-by-case basis.
- Mixed case will be used for all titles, footnotes, column headers, and programmer-supplied formats, as appropriate.

12.2.2. Headers

- All output should have the following header at the top left of each page:

Emalex Biosciences, Inc
Protocol EBS-101-OL-001
- All output should have Page n of N at the top or bottom right corner of each page. TFLs are internally paginated in relation to the total length (i.e., the page number should appear sequentially as page n of N, where N is the total number of pages in the table).
- The date output was generated should appear along with the program name as a footer on each page.

This document is confidential.

12.2.3. Display Titles

- Each TFL is identified by the designation and a numeral. (i.e., Table 14.1.1). ICH E3 numbering is strongly recommended. A decimal system (x.y and x.y.z) is used to identify TFLs with related contents. The title is centered. The analysis set is identified on the line immediately following the title. The title and table designation are single spaced. A solid line spanning the margins will separate the display titles from the column headers. There will be 1 blank line between the last title and the solid line.

Table x.y.z
First Line of Title
Second Line of Title if Needed
(ITT Analysis Set)

12.2.4. Column Headers

- Column headings are displayed immediately below the solid line described above in initial upper-case characters.
- In the case of efficacy tables, the variable (or characteristic) column will be on the far left followed by the treatment group columns and total column (if applicable). P-values may be presented under the total column or in separate p-value column (if applicable). Within-treatment comparisons may have p-values presented in a row beneath the summary statistics for that treatment.
- For numeric variables, include "unit" in column or row heading when appropriate.
- Analysis set sizes will be presented for each treatment group in the column heading as (N=xx) (or in the row headings, if applicable). This is distinct from the 'n' used for the descriptive statistics representing the number of subjects in the analysis set.

12.2.5. Body of the Data Display

12.2.5.1. General Conventions

Data in columns of a table or listing are formatted as follows:

- Alphanumeric values are left-justified;
- Numbers containing fractional portions are decimal aligned.

12.2.5.2. Table Conventions

- Units will be included where available.
- If the categories of a parameter are ordered, then all categories between the maximum and minimum category are presented in the table, even if n=0 for all treatment groups in a given category that is between the minimum and maximum level for that parameter. For example, the frequency distribution for symptom severity would appear as:

Severity Rating	N
mild	3
moderate	8
severe	0

Where percentages are presented in these tables, zero percentages will not be presented and so counts of 0 will be presented as 0 and not as 0 (0%).

This document is confidential.

- If the categories are not ordered (e.g., Medical History, Reasons for Discontinuation from the Study, etc.), then only those categories for which there is at least 1 subject represented in 1 or more groups are included.
- An Unknown or Missing category are added to each parameter for which information is not available for 1 or more subjects.
- Unless otherwise specified, the estimated mean and median for a set of values are printed out to 1 more significant digit than the original values, and standard deviations are printed out to 2 more significant digits than the original values. The minimum and maximum should report the same significant digits as the original values. For example, for systolic blood pressure:

N	XX
Mean (SD)	XX.X (XX.XX)
Median	XX.X
Min, Max	XX, XX

- P-values are output in the format: "0.xxx", where xxx is the value rounded to 3 decimal places. Every p-value less than 0.001 will be presented as <0.001. If the p-value are less than 0.0001, then present as <0.0001. If the p-value is returned as >0.999, then present as >0.999.
- Percentage values are printed to one decimal place, in parentheses with no spaces, one space after the count (e.g., 7 (12.8%), 13 (5.4%)). Pre-determine how to display values that round down to 0.0. A common convention is to display as '<0.1', or as appropriate with additional decimal places. Unless otherwise noted, for all percentages, the number of subjects in the analysis set for the treatment group who have an observation will be the denominator. Percentages after zero counts should not be displayed and percentages equating to 100% are presented as 100%, without decimal places.
- Unless otherwise specified, tabular display of data for medical history, prior/concomitant medications, and all tabular displays of adverse event data are presented by the body system, treatment class, or SOC with the highest occurrence in the overall group in decreasing order, assuming all terms are coded. Within the body system, drug class and SOC, medical history (by preferred term), drugs (by ATC code), and adverse events (by preferred term) are displayed in decreasing order. If incidence for more than 1 term is identical, they should then be sorted alphabetically. Missing descriptive statistics or p-values which cannot be estimated are reported as "—" .
- The percentage of subjects is normally calculated as a proportion of the number of subjects assessed in the relevant treatment group (or overall) for the analysis set presented. However, careful consideration is required in many instances due to the complicated nature of selecting the denominator, usually the appropriate number of subjects exposed. Describe details of this in footnotes or programming notes.
- For categorical summaries (number and percentage of subjects) where a subject can be included in more than one category, describe in a footnote or programming note if the subjects are included in the summary statistics for all relevant categories or just 1 category and the criteria for selecting the criteria.
- Where a category with a subheading (such as system organ class) has to be split over more than one page, output the subheading followed by "(cont)" at the top of each subsequent page. The overall summary statistics for the subheading should only be output on the first relevant page.

This document is confidential.

12.2.5.3. *Listing Conventions*

- Listings will be sorted for presentation in order of treatment groups as above, subject number, visit/collection day, and visit/collection time.
- Missing data are represented on subject listings as either a hyphen ("–") with a corresponding footnote ("– = unknown or not evaluated"), or as "N/A", with the footnote "N/A = not applicable", whichever is appropriate.
- Dates are printed in SAS DATE9.format ("ddMMMyyyy": 01JUL2000). Missing portions of dates are represented on subject listings as dashes (--JUL2000). Dates that are missing because they are not applicable for the subject are output as "N/A", unless otherwise specified.
- All observed time values are to be presented using a 24-hour clock HH:MM or HH:MM:SS format (e.g., 11:26:45, or 11:26). Time will only be reported if it was measured as part of the study.
- Units will be included where available.

12.2.5.4. *Figure Conventions*

- Unless otherwise specified, for all figures, study visits will be displayed on the X-axis and endpoint (e.g., treatment mean change from Baseline) values will be displayed on the Y-axis.

